8.1. Efficacy Assessments

Efficacy is not evaluated in this study.

8.2. Safety Assessments

Planned time points for all safety assessments are provided in the SoA in Section 1.3.

8.2.1. Physical Examinations

Physical examinations, height, weight, and BMI will be conducted according to the SoA in Section 1.3.

A complete physical examination will include, at a minimum, assessments of the dermatological, cardiovascular, respiratory, gastrointestinal, and neurological systems.

Symptom-directed physical examinations will also be performed.

Investigators should pay special attention to clinical signs related to previous serious illnesses.

8.2.2. Vital Signs

For each participant, vital signs measurements should be conducted according to the SoA in Section 1.3. If warranted, additional vital signs may be measured.

Blood pressure and pulse rate should be measured after at least 5 minutes sitting. When possible, measurements of blood pressure and pulse rate should be performed at approximately the same time of day at each scheduled time point.

If orthostatic measurements are required, participants should be supine for at least 5 minutes and measurement obtained between 2 to 3 minutes after standing.

If the participant feels unable to stand, supine vital signs only will be recorded.

Unscheduled orthostatic vital signs should be assessed, if possible, during any AE of *Dizziness* or posture-induced symptoms. Additional vital signs may be measured throughout the study per investigator discretion.

8.2.3. Electrocardiograms

For each participant, a single 12-lead digital ECG will be collected according to the SoA in Section 1.3. All single ECGs recorded should be stored at the investigational site. ECGs may be obtained at additional times when deemed clinically necessary, for example, to assess participants' safety.

During the study, ECGs should be recorded before collecting any blood samples. Participants must be supine for at least 5 to 10 minutes before ECG collection, and remain supine and awake during ECG collection.

Any clinically significant findings from ECGs that result in a diagnosis and that occur after the participant receives the first dose of study intervention should be reported to the sponsor, or its designee, as an AE via the eCRF.

ECGs will be interpreted by the investigator (a physician or qualified designee) at the site as soon after the time of ECG collection as practical, and ideally while the participant is still present, to determine whether the participant meets entry criteria at the relevant visit(s) and for immediate participant management, should any clinically relevant findings be identified.

8.2.4. Clinical Safety Laboratory Tests

See Section 10.2 for the list of clinical laboratory tests to be performed and the SoA for the timing and frequency.

The investigator must review the laboratory results, document this review, and report any clinically relevant changes occurring during the study as an AE. The laboratory results must be retained with source documents unless a source document agreement or comparable document cites an electronic location that accommodates the expected retention duration.

Clinically significant abnormal laboratory findings are those which are not associated with the underlying disease, unless judged by the investigator to be more severe than expected for the participant's condition.

All laboratory tests with values considered clinically significantly abnormal during participation in the study should be repeated until the values return to normal or baseline or are no longer considered clinically significant by the investigator or medical monitor.

If such values do not return to normal/baseline within a period of time judged reasonable by the investigator, the etiology should be identified and the sponsor notified.

All protocol-required laboratory assessments, as defined in Section 10.2, must be conducted in accordance with the SoA, standard collection requirements, and laboratory manual.

If laboratory values from non-protocol specified laboratory assessments performed at an investigator-designated local laboratory require a change in participant management or are

considered clinically significant by the investigator, for example, SAE or AE or dose modification, then report the information as an AE.

8.2.5. Pregnancy Testing

Pregnancy testing will be performed as detailed in the SoA in Section 1.3.

8.2.6. Safety Monitoring

8.2.6.1. Hepatic Safety Monitoring and Evaluation

This table summarizes actions to take based on abnormal hepatic laboratory or clinical changes.

Participants with normal or near normal baseline (ALT, AST, or ALP $<1.5 \times$ ULN)

If this laboratory value is observed...	Then...	
	Initiate or continue close hepatic monitoring	Initiate comprehensive evaluation
ALT or AST $\geq 3 \times$ ULN	X	
ALP $\geq 2 \times$ ULN	X	
TBL $\geq 2 \times$ ULN ^b	X	
ALT or AST $\geq 5 \times$ ULN	X	X
ALP $\geq 2.5 \times$ ULN	X	X
ALT or AST $\geq 3 \times$ ULN with hepatic signs or symptoms ^a	X	X
ALT or AST $\geq 3 \times$ ULN and TBL $\geq 2 \times$ ULN ^b or INR ≥ 1.5	X	X

^a Examples of hepatic signs or symptoms: severe fatigue, nausea, vomiting, right upper quadrant abdominal pain, fever, rash, and/or eosinophilia $>5\%$.

^b In participants with Gilbert's syndrome the threshold for TBL may be higher.

8.2.6.1.1. *Close Hepatic Monitoring*

If a participant develops any one of these changes, initiate close hepatic monitoring:

ALT or AST $\geq 3 \times$ ULN or
ALP $\geq 2 \times$ ULN or
TBL $\geq 2 \times$ ULN ^b

^b In participants with Gilbert's syndrome the threshold for TBL may be higher.

Close hepatic monitoring should include these actions:

- Laboratory tests detailed in Section 10.6, including ALT, AST, alkaline phosphatase, TBL, direct bilirubin, gamma-glutamyl transferase, creatine kinase, and complete blood count with differential, should be checked within 48 to 72 hours of the detection of elevated liver tests to confirm the abnormality and to determine if it is increasing or decreasing.
- If the abnormality persists, clinical and laboratory monitoring should continue at a frequency of 2 to 3 times weekly until levels normalize or return to approximate baseline values.
- In addition to laboratory tests, basic evaluation for possible causes of abnormal liver tests should be initiated by the investigator in consultation with the Lilly-designated medical monitor. At a minimum, this evaluation should include physical examination and a thorough medical history, including current symptoms, recent illnesses (for example, heart failure, systemic infection, hypotension, or seizures), recent travel, concomitant medications (including over-the-counter), herbal and dietary supplements, history of alcohol drinking and other substance abuse.

8.2.6.1.2. *Comprehensive Hepatic Monitoring*

If a participant develops any one of the following laboratory or clinical changes, initiate a comprehensive hepatic evaluation:

ALT or AST $\geq 5 \times$ ULN or
ALP $\geq 2.5 \times$ ULN or
ALT or AST $\geq 3 \times$ ULN with hepatic signs or symptoms ^a or
ALT or AST $\geq 3 \times$ ULN and TBL $\geq 2 \times$ ULN ^b or INR ≥ 1.5

^a Examples of hepatic signs or symptoms: severe fatigue, nausea, vomiting, right upper quadrant abdominal pain, fever, rash, and/or eosinophilia $>5\%$.

^b In participants with Gilbert's syndrome the threshold for TBL may be higher.

Comprehensive hepatic evaluation should include these actions:

- At a minimum, comprehensive hepatic evaluation should include physical examination and a thorough medical history, as outlined above, as well as tests for prothrombin time-INR; tests for viral hepatitis A, B, C, and E; tests for autoimmune hepatitis; and an abdominal imaging study (for example, ultrasound or computed tomography scan).
- Based on the participant's history and initial results, further testing should be considered in consultation with the Lilly-designated medical monitor, including tests for hepatitis D virus, cytomegalovirus, Epstein-Barr virus, acetaminophen levels, acetaminophen protein adducts, urine toxicology screen, Wilson's disease, blood alcohol levels, urinary ethyl glucuronide, and blood phosphatidylethanol.
- Based on the circumstances and the investigator's assessment of the participant's clinical condition, the investigator should consider referring the participant for a hepatologist or gastroenterologist consultation, and additional tests including magnetic resonance cholangiopancreatography, endoscopic retrograde cholangiopancreatography, cardiac echocardiogram, or a liver biopsy.
- Clinical and laboratory monitoring should continue at a frequency of 1 to 2 times weekly until levels normalize or return to approximate baseline values.
- All the medical information and test results related to the hepatic monitoring and comprehensive hepatic evaluation should be collected and recorded in a hepatic safety CRF.

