10.2. Appendix 2: Clinical Laboratory Tests

The tests detailed in the table below will be performed by the central or local laboratory as specified below.

In circumstances where the sponsor approves local laboratory testing in lieu of central laboratory testing (in the table below), the local laboratory must be qualified in accordance with applicable local regulations.

Protocol-specific requirements for inclusion or exclusion of participants are detailed in Section 5 of the protocol.

Additional tests may be performed at any time during the study as determined necessary by the investigator or required by local regulations.

Investigators must document their review of the laboratory safety results.

Clinical Laboratory Tests	Comments
Hematology	Performed locally at screening and Day -1 and centrally at Day 1 predose and all postdose time points unless otherwise stated. *reported as required.
Hematocrit Hemoglobin Erythrocyte count Mean cell volume Mean cell hemoglobin Mean cell hemoglobin concentration Leukocytes Cell morphology* Platelets	Absolute counts and/or % of: Neutrophils Lymphocytes Monocytes Eosinophils Basophils
Clinical Chemistry	Performed locally at screening and Day -1 and centrally at Day 1 predose and all postdose time points unless otherwise stated.
Sodium Potassium Calcium Phosphorous Glucose (random) Blood urea nitrogen Uric acid	Total cholesterol Total protein Albumin Total bilirubin Direct bilirubin Alkaline phosphatase Aspartate aminotransferase Alanine aminotransferase Creatinine
Urinalysis	Performed locally at screening and Day -1 and centrally at Day 1 predose and all postdose time points unless otherwise stated.
Specific gravity pH Protein Glucose Ketones Leukocyte esterase	Bilirubin Urobilinogen Blood Nitrite Microscopy (if dipstick abnormal; blood, protein, nitrites, or leukocyte esterase is positive)

Clinical Laboratory Tests		Comments
Hormones (participants assigned female at birth)		Performed by a local laboratory.
Serum and urine pregnancy test	Follicle-stimulating hormone test	
Other		Performed by a local laboratory.
Breath or urine ethanol test	Urine drug screen	
TB, HIV, and hepatitis serology		Performed by a local laboratory. a If hepatitis B core antibody is positive, further testing for hepatitis B DNA will be performed. b If hepatitis C antibody is positive, further testing for hepatitis C virus RNA will be performed.

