10.6. Appendix 6: Liver Safety: Suggested Actions and Follow-up Assessments

Hepatic Evaluation Testing

See Section 8.2.6.1 for guidance on appropriate test selection.

The Lilly-designated central laboratory should complete the analysis of all selected testing except for testing listed in the investigator-designated local laboratory table. The central laboratory will report results if a validated test or calculation is available.

Local testing may be performed in addition to central testing when necessary for immediate participant management. The local laboratory must be qualified in accordance with applicable local regulations. If testing is not available in certain regions based on local requirements, consult with Lilly-designated medical monitor.

Tests assayed by Lilly-designated central laboratory	
Hepatic Hematology Panel	Hepatitis A virus (HAV) testing:
Hemoglobin	HAV total antibody ^a
Hematocrit	HAV IgM antibody
Erythrocytes (RBCs - red blood cells)	Hepatitis B virus (HBV) testing:
Leukocytes (WBCs - white blood cells)	Hepatitis B surface antigen (HBsAg)
Differential:	Hepatitis B surface antibody (anti-HBs)
Neutrophils	Hepatitis B core total antibody (anti-HBc)
Lymphocytes	Hepatitis B core IgM antibody
Monocytes	HBV DNA ^b
Basophils	Hepatitis C virus (HCV) testing:
Eosinophils	HCV total antibody ^a
Platelets	HCV RNA ^b
Cell morphology (RBC and WBC)	Hepatitis D virus (HDV) testing:
Hepatic Clinical Chemistry Panel	HDV total antibody ^a
Total bilirubin	HDV IgM antibody
Direct bilirubin	HDV RNA ^b
Alkaline phosphatase (ALP)	Hepatitis E virus (HEV) testing:
Alanine aminotransferase (ALT)	HEV IgG antibody
Aspartate aminotransferase (AST)	HEV IgM antibody
Gamma-glutamyl transferase (GGT)	HEV RNA ^b
Creatine kinase (CK)	Anti-nuclear antibody (ANA)
Hepatic Coagulation Panel	Anti-smooth muscle antibody (ASMA) or anti-actin antibody
Prothrombin time, INR (PT-INR)	Immunoglobulin IgA (quantitative)
Urine Chemistry	Immunoglobulin IgG (quantitative)
Drug screen	Immunoglobulin IgM (quantitative)
Haptoglobin	

Tests assayed ONLY by investigator-designated local laboratory	
Acetaminophen	Cytomegalovirus (CMV) testing:
Acetaminophen protein adducts ^c	CMV antibody
Alkaline phosphatase isoenzymes	CMV DNA ^b
Ceruloplasmin	Herpes simplex virus (HSV) testing:
Copper	HSV (Type 1 and 2) antibody
Ethyl alcohol (ethanol, EtOH)	HSV (Type 1 and 2) DNA ^b
Phosphatidylethanol (PEth)	Liver kidney microsomal type 1 (LKM-1) antibody
Urine Chemistry	Microbiology Culture:

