4.4.7. Hepatic Monitoring

If a participant experiences elevated hepatic laboratory parameters, as detailed in Section 8.2.6.1 of the protocol, additional tests will be performed to confirm the abnormality. Additional safety

data may be collected if required, as defined in the protocol. Where applicable, the following will be presented.

The participants' liver disease history and associated person liver disease history data will be listed if data warrants. Use of acetaminophen during the study, which has potential for hepatotoxicity, will be listed. Results from any hepatic monitoring procedures, such as a magnetic resonance elastography scan, and biopsy assessments will be listed, if performed.

Hepatic risk factor assessment data will be listed. Liver related signs and symptoms data may be summarized by treatment. Any known alcohol and recreational drug use data will also be listed.

Hepatic chemistry, hematology, coagulation, and serology values outside the reference ranges will be flagged on the individual participant data listings as part of the listing mentioned in Section 4.4.4.

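### Protocol 8.2.6.1.2 allows once-weekly follow-up of the more serious liver-test abnormalities, below the twice-weekly minimum of the close monitoring that the action table also requires for them

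*Protocol*

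**What the plan says.** The rules are in Protocol 8.2.6.1, for participants whose baseline ALT, AST or ALP is below 1.5 × ULN.

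- **Action table.** It has two action columns. The first is headed "Initiate or continue close hepatic monitoring" and is marked in all 7 rows. The second, for comprehensive evaluation, is marked in 4 of those rows.
- **8.2.6.1.1, close monitoring.** A panel of liver and related tests "should be checked within 48 to 72 hours of the detection of elevated liver tests to confirm the abnormality". Then: "If the abnormality persists, clinical and laboratory monitoring should continue at a frequency of 2 to 3 times weekly until levels normalize". The bullet goes on to accept a return to near baseline as the alternative end point.
- **8.2.6.1.2, comprehensive evaluation.** After the work-up, further tests and possible specialist referral, it says: "Clinical and laboratory monitoring should continue at a frequency of 1 to 2 times weekly until levels normalize or return to approximate baseline values".

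Two other places could have set an order between these rules. Protocol 10.6 (Appendix 6) says only "See Section 8.2.6.1 for guidance on appropriate test selection" and lists tests. SAP 4.4.7 says "If a participant experiences elevated hepatic laboratory parameters, as detailed in Section 8.2.6.1 of the protocol, additional tests will be performed" and gives no frequency.

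**The concern.** The comprehensive tier is for larger, symptomatic or combined abnormalities, yet its stated minimum frequency is lower than that of the milder tier. An asymptomatic participant with persistent ALT at 3 × ULN should be checked at least twice a week. One with ALT at 5 × ULN, or at 3 × ULN with symptoms or with bilirubin at 2 × ULN, may be checked once a week by a site that follows the 8.2.6.1.2 bullet. The protocol gives no reason for this ordering.

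The participants are healthy volunteers who can expect no therapeutic benefit (Protocol 2.3), and the study is multi-center, so sites may read the rules differently. What is at stake is how soon a worsening abnormality would be noticed. The primary pharmacokinetic comparison is not involved.

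**Working it through.** The plan states no figure to reproduce here. The check is a comparison of the texts with simple arithmetic.

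**1. Do both rules apply to the same participants?**

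| Action table row | Close monitoring | Comprehensive evaluation |
|---|---|---|
| ALT or AST ≥3 × ULN | yes | no |
| ALP ≥2 × ULN | yes | no |
| TBL ≥2 × ULN | yes | no |
| ALT or AST ≥5 × ULN | yes | yes |
| ALP ≥2.5 × ULN | yes | yes |
| ALT or AST ≥3 × ULN with hepatic signs or symptoms | yes | yes |
| ALT or AST ≥3 × ULN and TBL ≥2 × ULN or INR ≥1.5 | yes | yes |

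Close monitoring is marked in 7 of 7 rows, and both actions in 4 of 7. The thresholds listed in 8.2.6.1.1 lead to the same place: three of the four comprehensive rows always meet them. The fourth does too, unless it is read as letting an isolated INR of 1.5 or more qualify.

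**2. Do the rules cover the same activity and period?** Both concern clinical and laboratory monitoring, and both end at normal or near-baseline values. The one difference is that the 8.2.6.1.1 frequency depends on the abnormality persisting at the 48 to 72 hour recheck. If it does not persist, the rules need not clash, and this point does not cover that case.

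**3. Where do the ranges meet?** Close monitoring is 2 to 3 a week and the comprehensive section 1 to 2 a week.

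| Checks a week | Average gap (7 ÷ checks) | Meets 8.2.6.1.1 | Meets 8.2.6.1.2 |
|---|---|---|---|
| 1 | 7 days | no | yes |
| 2 | 3.5 days | yes | yes |
| 3 | 2.3 days | yes | no |

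Only twice weekly meets both. Once weekly gives half the close-monitoring minimum and doubles the longest average gap, from 3.5 to 7 days.

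**4. Does other text settle it?** Appendix 6 and SAP 4.4.7 give no frequency. Protocol 8.2.4 asks for clinically significant abnormal results to be repeated until they resolve or cease to matter, without an interval. Nothing describes 1 to 2 times weekly as a later step-down.

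**5. Does routine sampling cover the gap?** No. Protocol 10.2 has chemistry done "centrally at Day 1 predose and all postdose time points", and Protocol 10.2.1 budgets 5 central hematology and chemistry samples. Taking off the predose sample leaves 5 − 1 = 4 postdose samples from Day 1 to Day 71. Follow-up of an abnormality therefore depends on the 8.2.6.1 rules.

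**The case against.** The strongest reply is that the table already answers the question. It tells sites to start or continue close monitoring in every comprehensive row, so the evaluation is added to close monitoring and does not replace it. Escalation is not one of the end points in 8.2.6.1.1. On that reading, 2 to 3 times weekly stays in force and a site that checks twice weekly meets both rules. Nor can a site easily use 8.2.6.1.2 alone: it refers back for history and examination, and the list of liver tests to repeat is in 8.2.6.1.1. The lower-frequency bullet also comes last, after the work-up and referral, so it could describe later follow-up.

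There are further limits on harm. Both frequencies are worded as recommendations, and the medical monitor is consulted in both tiers. Protocol 10.2 says "Additional tests may be performed at any time during the study as determined necessary by the investigator". With a single dose, no later dosing decision waits on a recheck.

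Most of this stands, and it keeps the severity low. It does not remove the conflict. If close monitoring continues, the once-weekly option in 8.2.6.1.2 contradicts it. If the option is a step-down, the condition for stepping down is missing, and both rules run to the same end point. Discretion to test more often does not say which minimum applies.

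**Conclusion.** The concern holds. While a liver-test abnormality persists, once-weekly monitoring is permitted by 8.2.6.1.2 but falls below the minimum that the action table and 8.2.6.1.1 set for the same participants: 1 check a week against 2. The conflict is confined to the once-weekly option and to abnormalities that persist at the recheck.

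These figures describe the two written ranges and do not measure risk. The documents give neither a rate of liver-test elevation nor a time to normalisation, and I assume that few participants would be affected. This is a low-severity inconsistency between safety rules that is worth correcting. It has no bearing on the sample size or the bioequivalence conclusion.

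**What to change.** Add one sentence to the last part of Protocol 8.2.6.1.2, for example: *While the abnormality persists, the 2 to 3 times weekly frequency in 8.2.6.1.1 continues.* This agrees with what the action table already implies and removes the lower minimum for the higher tier.

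A protocol amendment or a clarification letter to sites would be enough. The cost is that sentence and a few more blood draws in the few participants who trigger comprehensive evaluation. The SAP needs no change, because section 4.4.7 defers to Protocol 8.2.6.1.

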8.2.7. Hypersensitivity Reactions

Many drugs, including oral agents and biologic agents, carry the risk of systemic hypersensitivity reactions. If such a reaction occurs, additional data should be provided to the sponsor in the designated CRFs.

Sites should have appropriately trained medical staff and appropriate medical equipment available when study participants are receiving study intervention. It is recommended that participants who experience a systemic hypersensitivity reaction be treated per national and international guidelines.

In the case of a suspected systemic hypersensitivity event, additional blood samples should be collected as described in Section 10.2.2. Laboratory results are provided to the sponsor via the central laboratory.

8.2.8. Tuberculosis Testing and Monitoring

Participants will be tested as indicated in the SoA, in Section 1.3, for evidence of active or latent TB using the QuantiFERON-TB Gold test. If the test is indeterminate, 1 retest is allowed. If the retest is indeterminate, the participant will be excluded from the study.

Participants who have had household contact with a person with active TB must be excluded, unless appropriate and documented prophylaxis treatment for TB has been completed at least 3 months prior to treatment.

Participants with any history of active TB are excluded from the study, regardless of previous or current TB treatments.

8.2.9. Injection-Site Reactions

Although there will be no prospective collection of ISR information, spontaneously reported ISRs by the participant will be recorded as AEs, with the ISR CRF used to collect supplemental data on the following specific findings:

- induration
- pain
- edema
- pruritus, and
- erythema.

The findings of ISR for a specific injection will be captured as a single AE of *Injection-site reaction*, if 1 or more than 1 of the findings is positive, and the severity that is recorded on the ISR AE form will be the highest severity across the findings at each applicable visit.

If injection-site pain is reported at any time during the study, the intensity of pain will be quantified using the 100-mm validated pain VAS. The VAS is a well validated tool (Williamson and Hoggart 2005) to assess injection-site pain; it is presented as a 100-mm line anchored by verbal descriptors, usually “no pain” and “worst imaginable pain.” The participant will be asked to rate any pain at the injection site on a scale of 0 to 100 on the line as soon as is practical following reporting of the event.

Injection-site assessments should be conducted at the next planned visit following the reporting of an injection-related AE.

